6.2. Preparation/Handling/Storage/Accountability

Preparation/Handling/Storage

All study intervention must be stored as specified on the product-specific labeling.

Refer to the pharmacy manual/study site investigational product and procedures manual for additional guidance on study intervention preparation, handling, and storage.

Accountability

The investigator is responsible for ensuring that all study intervention received at the site is inventoried and accounted for throughout the study.

The dispensing of study intervention to the participant, and the return of study intervention from the participant (if applicable), must be documented on the intervention accountability form. Participants must be instructed to return all original containers, whether empty or containing study intervention. All study intervention will be stored and disposed of according to the sponsor's instructions. Study-site personnel must not combine contents of the study intervention containers.

Study intervention must be handled in strict accordance with the protocol and as indicated on the container label, and must be stored at the study site in a limited-access area or in a locked cabinet under appropriate environmental conditions. Unused study intervention, and study intervention returned by the participant, must be available for verification by the sponsor's study site monitor during on-site monitoring visits. The return to the sponsor of unused study intervention, or used returned study intervention for destruction, will be documented on the intervention return form. When the study site is an authorized destruction unit and study intervention supplies are destroyed on-site, this must also be documented on the intervention return form.

Potentially hazardous materials such as used ampules, needles, syringes and vials containing hazardous liquids, must be disposed of immediately in a safe manner and therefore will not be retained for intervention accountability purposes.

Study intervention must be dispensed under the supervision of the investigator or a qualified member of the study-site personnel, or by a hospital/clinic pharmacist. Study intervention will be supplied only to participants participating in the study. Returned study intervention must not be dispensed again, even to the same participant. An intermediate study intervention compliance check is not considered to be a re-dispensing. Study intervention may not be relabeled or reassigned for use by other participants. The investigator agrees neither to dispense the study intervention from, nor store it at, any site other than the study sites agreed upon with the sponsor. Further guidance and information for the final disposition of unused study interventions are provided in the Site Investigational Product Procedures Manual.

6.3. Measures to Minimize Bias: Randomization and Blinding

Intervention Allocation

Procedures for Randomization and Stratification

Central randomization will be implemented in this study. Participants will be randomly assigned to 1 of 2 intervention arms of each part of the study with ratio 4:1 (JNJ-3989 + NA: placebo + NA) based on a computer-generated randomization schedule prepared before the study by or under the supervision of the sponsor.

The randomization will be balanced by using randomly permuted blocks and will be stratified by the presence of compensated cirrhosis at screening (yes or no, Part 1 only), HDV RNA testing laboratory location (China versus outside of China), and HBeAg status at screening (positive versus negative). The IWRS will assign a unique intervention code, which will dictate the intervention assignment and matching study intervention kit for the participant. The requestor must use his or her own user identification and personal identification number when contacting the IWRS, and will then give the relevant participant details to uniquely identify the participant.

Blinding

Blinded treatment will be used to reduce potential bias during data collection and evaluation of clinical endpoints.

The investigators, participants, and all site personnel will remain blinded to study intervention allocation until a participant has completed the Week 48 visit or has discontinued earlier. When a participant has completed the Week 48 visit or discontinued earlier, the investigator, site personnel, sponsor, and participants will be unblinded for treatment allocation and all laboratory data, including HDV RNA and HBsAg data. After Week 48, it will be communicated to the investigators whether the participant was allocated to either the immediate active arm (Arm 1) or the deferred active arm (Arm 2) to allow that the participant follows the correct visit schedule during the open-label phase (see Section 1.3.2, Schedule of Activities – Open-label Study Intervention Phase (Weeks 52 – EOT)).

As of Week 52 and up and until the end of the study intervention phase, study intervention will be administered in open-label fashion to all participants and efficacy results (eg, HDV RNA and HBsAg data) will be reported to the sites.

The Sponsor Committee will be unblinded to treatment allocation in the initial exploration of the antiviral activity criteria in up to 16 participants randomized in Part 1, based on aggregate interim data of HDV RNA and/or individual HDV RNA profiles and HBsAg data where the individual participant identification will be masked. This is to assess whether the evaluation of antiviral activity on a small number of participants warrants to expand enrollment to the remaining 30 participants (start of Part 2).

At the time of Part 1 IA1 (when all participants of Part 1 have completed at least Week 16 or discontinued earlier), sponsor personnel and members of the IFLEP will become unblinded to the Part 1 data. However, as soon as Part 2 commences, all sponsor personnel, including the Sponsor Committee, and the members of the IFLEP remain blinded to subsequent IDMC data reviews during the double-blind phase. During the open-label phase, all data will be unblinded (see Section 9.5). Study site personnel, investigators, participants, and operational sponsor team members involved with the sites will have no access to any of the evaluations performed by either the sponsor or the IDMC. For safety-related decisions, HDV RNA and HBsAg data may be discussed with investigators on a case-by-case basis.

The investigator may in an emergency determine the identity of the study intervention by contacting the IWRS. While the responsibility to break the study intervention code in emergency situations resides solely with the investigator, it is recommended that the investigator contacts the sponsor or its designee to discuss the particular situation, before breaking the blind, only if this does not delay action with respect to treatment in an emergency situation. Telephone contact with the sponsor or its designee will be available 24 hours per day, 7 days per week. In the event the blind is broken, the sponsor must be informed as soon as possible. The date and reason for the unblinding must be documented in the appropriate section of the CRF. The documentation received from the IWRS indicating the code break must be retained with the participant's source documents in a secure manner.

In case of IWRS participant unblinding and if the investigator requires to be unblinded in case of an emergent safety event (ie, study intervention discontinuation due to ALT flares) to allow further treatment of the participant, a sponsor request can be made to have the investigator and sponsor unblinded to all HDV RNA and HBsAg data from the double-blind phase.

During the blinded study treatment phase, HBV/HDV RNA, HBsAg, HBeAg, HBcrAg, anti-HBs, and anti-Hbe antibody tests cannot be done locally.

6.4. Study Intervention Compliance

Preparation of JNJ-3989/placebo, including the necessary blinding, will be performed by an unblinded preparer. JNJ-3989/placebo will be administered as a SC injection by the blinded administrator.

An optional medication diary to document oral study intervention intake can be made available for participants with an observed or known risk for study intervention non-compliance. The completed diaries are reviewed by the site staff and discussed with the participants for compliance monitoring and counseling. Completed diaries will be returned to the site staff to add to the source documents.

The participants will be requested to bring unused oral study interventions and empty packaging to the study site at each visit.

Every effort should be made to have the participant take the (oral) study interventions as indicated in the [Schedule of Activities](#).

- If an injection of JNJ-3989 was missed, the injection should be given as soon as possible but within 3 weeks after the scheduled time. Otherwise, the injection should be skipped, and the next injection should be given at the next scheduled time point per the initial injection schedule.

Note: All missed injections and significant delays should be discussed with the sponsor.

- If a dose of NA is missed, the participant should follow the guidelines in the package insert.

If a participant's study intervention intake is not according to the protocol, the investigator will take the necessary measures to ensure future adherence to the protocol.

Per Protocol Amendment 5, NA treatment will be continued in all participants in Part 2 until the last study visit.

If clinically indicated, switching from one NA treatment (ETV, tenofovir disoproxil, or TAF) to another NA treatment (ETV, tenofovir disoproxil, or TAF) during the study is allowed for all participants after consultation with the sponsor.

6.5. Re-treatment With NA During the Follow-up Phase

Participants who complete treatment with JNJ-3989 at the end of the open-label phase^a in Part 1 and Part 2 will be closely monitored for transaminase flares and for HBV/HDV recurrence during the follow-up phase.

Before Protocol Amendment 5, NA treatment should be continued during the entire follow-up phase according to treatment guidelines for cirrhotic patients. For non-cirrhotic patients, NA treatment should be continued until the last study visit (including the visit in the follow-up phase) unless confirmed HBsAg seroclearance, ALT <3x ULN, and HBV DNA <LLOQ is observed, in which case NA treatment may be discontinued upon discussion with the sponsor.

^a At Week 144 (Arms 1) or Week 148 (Arms 2) in Part 1 and Part 2 before Protocol Amendment 5; at Week 96 or later (Arm 1) or Week 100 or later (Arm 2) in Part 2 after Protocol Amendment 5

Per Protocol Amendment 5, NA treatment will be continued in all participants in Part 2 until the last study visit (including visit in the follow-up visit).

6.5.1. Re-treatment With NA

Amongst the non-cirrhotic participants who stop treatment with NA, NA treatment will be restarted if any of the following criteria are met:

- If there are signs of decreasing liver function based on laboratory findings (INR or direct bilirubin) or clinical assessment.
- HBeAg seroreversion among participants who had previously experienced HBeAg loss.
- Post-treatment values of HBV DNA >2,000 IU/mL and ALT >5x ULN
- Post-treatment values of HBV DNA >20,000 IU/mL.

Earlier restarting of NA treatment is at the investigator's discretion, even if the above criteria are not met yet.

Per Protocol Amendment 5, NA treatment will be continued in all participants in Part 2 until the last study visit (including visit in the follow-up phase).

6.6. Treatment of Overdose

For this study, any dose of JNJ-3989 exceeding the protocol-specified dose with $\geq 25\%$ (refer to Section 6.1) will be considered an overdose. Any dose of NA greater than the prescribed dose (refer to Section 6.1) will be considered an overdose.

In the event of an overdose, the investigator or treating physician should:

- Contact the Medical Monitor immediately.
- Closely monitor the participant for AE/SAE and laboratory abnormalities.
- Obtain a plasma sample for PK analysis as soon as possible from the date of the last dose of study intervention if requested by the Medical Monitor (determined on a case-by-case basis).
- Document the quantity of the excess dose as well as the duration of the overdosing in the CRF.
- Decisions regarding dose interruptions or modifications will be made by the investigator in consultation with the Medical Monitor based on the clinical evaluation of the participant.

6.7. Concomitant Therapy

Pre-study therapies administered up to 30 days before first dose of study intervention, as well as any prior IFN use, must be recorded at screening. If applicable, the participant's last anti-HBV and/or anti-HDV treatment prior to screening must also be recorded.

Concomitant therapies must be recorded throughout the study, from signing of the ICF up to the last study visit. Concomitant therapies must also be recorded beyond the last study visit only in conjunction with new or worsening (S)Aes.

Note that locally approved COVID-19 vaccines (including those that received emergency use authorization or conditional marketing authorization) are allowed throughout the study.

All COVID-19 vaccination-related data (eg, COVID-19 vaccination, AEs, AE management) should be appropriately captured in the CRF and source documents. Refer to the COVID-19 vaccine prescribing information for more details.

All therapies (prescription or over-the-counter medications, including vaccines, vitamins, herbal supplements; non-pharmacologic therapies such as electrical stimulation, acupuncture, special diets, exercise regimens, or other specific categories of interest) different from the study intervention must be recorded in the CRF. Recorded information will include a description of the type of therapy, duration of use, dosing regimen, route of administration, and its indication. Modification of an effective pre-existing therapy should not be made for the explicit purpose of entering a participant into the study.

An overview of disallowed medication is provided in [Table 2](#).

Table 2: Disallowed Medication

Disallowed at any time prior to screening until end of follow-up^a:

- Any oligonucleotide-based treatment (eg, siRNA, nucleic acid polymers, and antisense oligonucleotides), other than the study intervention taken in the context of this study.
-

Disallowed from 6 months prior to screening until end of follow-up^a:

- Any anti-HBV/HDV drug (including vaccines, interferons) other than the study intervention taken in the context of this study.
Note: Study intervention taken in the context of this study (ETV, TD, TAF) is allowed. Prior hepatic treatment with herbal or nutritional products is also allowed but should be stopped at screening.
 - Any investigational agent, investigational vaccine, invasive investigational medical device, or investigational biological product (other than the study intervention taken in the context of this study)
Note: For investigational COVID-19 vaccines administered within 6 months prior to screening, an exception will be made as long as the vaccine has been approved (or received emergency use authorization or conditional marketing authorization) at the time of screening.
-

Disallowed from 6 months prior to baseline until end of follow-up^a:

- Any systemically (eg, intravenously, intramuscularly, orally, subcutaneously) administered medication that directly or indirectly interferes with immune responses (eg, cyclosporine, interleukins, systemic corticosteroids exceeding 5 mg of prednisolone equivalent/day).
-

Disallowed from 1 month prior to screening until end of follow-up^a:

- Any medication that reduces renal function or competes for active tubular secretion (eg cimetidine, probenecid, quinidine).
-

Table 2: Disallowed Medication**Disallowed from screening until end of follow-up^a:**

- Biotin (>1 mg daily dose), either taken alone or as part of a multivitamin formulation.
Note: The use of other vitamins is allowed.
- Topical steroids (>7 days) under occlusive dressing.

^a Refer to Section 4.1 for the end of follow-up definition before and after Protocol Amendment 5.

Note: The list of disallowed medication is not exhaustive; for products falling in one of the categories and not mentioned by name, the sponsor should be contacted to determine whether the product can be allowed.

Note: Anticoagulants are to be used with caution. Aspirin and other antiplatelet aggregating agents are allowed. Further restrictions apply to participants undergoing optional liver biopsy procedures. Antiplatelet aggregating agents should be paused at least 9 days prior to liver biopsy procedures or according to local standard practice.

The sponsor must be notified in advance (or as soon as possible thereafter) of any instances in which prohibited therapies are administered.

The prescribing information for ETV, tenofovir disoproxil, and TAF should be consulted for any additional prohibited medication.

The sponsor must be notified in advance (or as soon as possible thereafter) of any instances in which prohibited therapies are administered.

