2.3.3. Benefit-risk Assessment for Study Participation

Based on the available data and proposed safety measures, the overall risk/benefit assessment for JNJ-3989 clinical studies is considered favorable for the following reasons:

- Overall, JNJ-3989 administration was safe and well tolerated in completed and ongoing studies, all of which (except REEF-D) are in CHB patients or healthy participants.
- Events of Special Interest are significant AEs that are judged to be of special interest because of clinical importance, known class effects or based on nonclinical signals. Events of Special Interest that will be carefully monitored during the study include ISRs, ALT/AST elevations, renal complications, hematologic abnormalities, and events related to cholesterol increase (Section 8.3.6, Adverse Events of Special Interest and Section 8.2.4, Clinical Safety Laboratory Assessments). In addition, the following toxicities will also be carefully monitored: rash and acute systemic allergic reactions (Section 8.3.6, Adverse Events of Special Interest).
- Continued careful assessment of the safety, efficacy, and PK during treatment is included in this study.
- To minimize potential risk and stress to participants, the following measures are in place:
 - Utilization of selection criteria which exclude participants who may potentially be at higher risk of an AE (see Section 5, Study Population).
 - Participants with liver cirrhosis are not eligible for Part 2 of the study.
 - Additional criteria based on HBsAg and HDV RNA levels will be used for Part 2 to reduce the risk of ALT/AST elevations on-treatment.
 - Utilization of withdrawal criteria (see Section 7, Discontinuation of Study Intervention and Participant Discontinuation/Withdrawal). If a participant drops out due to withdrawal of consent, he/she retains the option to participate in the safety follow-up procedures.
 - Restriction of placebo + NA treatment to 52 weeks.
 - Inclusion of treatment discontinuation criteria for signs of hepatic decompensation (see Section 7.1).

- Individuals showing signs of decreasing liver function during study conduct will discontinue treatment with JNJ-3989/placebo and alternative treatment options outside the study will be considered in discussion with the sponsor.

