7. DISCONTINUATION OF STUDY INTERVENTION AND PARTICIPANT DISCONTINUATION/WITHDRAWAL

7.1. Discontinuation of Study Intervention

A participant's investigational study intervention (JNJ-3989/placebo) **must** be discontinued if any of the criteria listed below apply. In those cases, NA treatment should be continued.

- The participant withdraws consent to receive study intervention.
- The investigator believes that for safety reasons or tolerability reasons (eg, AE) it is in the best interest of the participant to discontinue study intervention.
- The participant becomes pregnant.
- The participant has a \geq grade 3 rash (see Section 10.5, Appendix 5, Rash Management) or allergic reaction (see Section 8.3.6.3).
- The participant has signs of hepatic decompensation (ie, clinical evidence of ascites, bleeding varices, or hepatic encephalopathy) or an increase in direct bilirubin $>1.5x$ ULN in combination with INR $\geq 1.5x$ ULN or albumin <3.0 g/dL. In this case treatment with JNJ-3989 should be discontinued and alternative treatment options (outside the study) should be considered in discussion with the sponsor.

- The participant has a confirmed \geq grade 3 estimated glomerular filtration rate (eGFR) abnormality and a drop from baseline of >10 mL/min/1.73 m², considered at least possibly related to JNJ-3989 that persists despite change of tenofovir disoproxil to ETV or TAF (if the patient was receiving tenofovir disoproxil). Change of NA treatment should be considered anytime, according to the prescribing information. (see Section 8.3.6.4).
- The participant has a confirmed QTcF prolongation (defined as a QTcF value of >500 ms, or an increase from baseline of >60 ms) at any given time point.
- The participant requires treatment with any of the disallowed medications listed in Section 6.7 and does not intend to discontinue treatment with the disallowed medication.
- The participant has confirmed HBV virologic breakthrough (ie, confirmed on-treatment HBV DNA increase by >1 log₁₀ IU/mL from nadir or confirmed on-treatment HBV DNA level >200 IU/mL in participants who had HBV DNA level $<$ LLOQ of the HBV DNA assay). In case of virologic breakthrough, changing the NA should be considered in consultation with the sponsor. Injection with JNJ-3989 will be stopped if the NA change does not result in a decrease in HBV DNA levels.
- The participant has ALT/AST elevations, as described in Section 8.3.6.1, Intervention-emergent ALT/AST Elevations.

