- Per IDMC recommendation, in Part 2, the participants with HBsAg values >10.000 IU/mL at screening or baseline, who were assigned to Arm 1 (placebo), will not roll-over to the open-label phase and will enter the follow-up phase.
- The participant of the placebo group should discontinue study intervention (cannot start JNJ-3989 in the open-label phase in Part 2, Arm 2) if he/she develops cirrhosis at the end of the double-blind phase (based on the Week 48 FibroScan assessment).

If a participant discontinues study intervention for any reason before the end of the double-blind phase, end-of-intervention assessments must be obtained. The participant will enter the follow-up phase and complete the follow-up schedule unless the participant withdraws consent. Participants who withdraw consent will be offered an optional safety follow-up visit (see Section 1.3). Study intervention assigned to the participant who discontinued study intervention may not be assigned to another participant.

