7.2. Participant Discontinuation/Withdrawal From the Study

A participant will NOT be automatically withdrawn from the study if he or she has to discontinue study intervention.

A participant will be withdrawn from the study for any of the following reasons:

- Lost to follow-up
- Withdrawal of consent
- Death

When a participant withdraws before study completion, the reason for withdrawal is to be documented in the CRF and in the source document. If the reason for withdrawal from the study is withdrawal of consent then no additional assessments are allowed.

Withdrawal of Consent

A participant declining to return for scheduled visits does not necessarily constitute withdrawal of consent. Alternate follow-up mechanisms that the participant agreed to when signing the consent form apply as local regulations permit.

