9.4.2.1. Primary Estimand

The main analysis of the primary endpoint will be addressed by using the following estimand attributes:

1. Study Intervention:

- Arm 1: JNJ-3989 + NA
- Arm 2: Placebo + NA

2. Study population: Participants 18 to 65 years of age, inclusive, with HBV/HDV co-infection

3. Variable: Response status defined as having HDV RNA decline $\geq 2 \log_{10}$ IU/mL from baseline or HDV RNA TND in combination with normal ALT at Week 48

4. Intercurrent events (ICEs):

- a. Treatment discontinuation prior to Week 48: if the participant discontinued treatment prior to Week 48 then the participant will be considered as non-responder (composite strategy).
- b. Selected major protocol deviations (identified as ICEs): participants who experienced major protocol deviations considered ICE and who have missing ALT and/or HDV RNA data for the primary endpoint at Week 48 will be considered as non-responders (composite strategy).
- c. Deaths prior to Week 48 are handled in a composite strategy as participants who die prior to Week 48 will be considered as non-responders.

5. Population level summary: Difference in proportion of responders between the 2 intervention arms (Arm 1-Arm 2).

Note: The SAP will list the major protocol deviations used for the purpose of efficacy analyses and flag those that are to be considered ICEs.

Assumptions:

- Missing Data for HDV RNA and ALT are Missing At Random (MAR)
- The treatment effect is homogeneous across strata.

Data Included

All available data from randomized participants that have received at least one dose is included (ITT analysis set in Part 2), after taking into account all the ICEs and applying the ICE strategies.

Missing Data Handling Rules

Participants who withdraw from the study prior to Week 48 will be considered as non-responders.

If a participant remains in the study after early discontinuing treatment or after experiencing a major protocol deviation (defined for the purpose of efficacy analyses and is an intercurrent event) and has missing Week 48 value for HDV RNA and/or ALT, then the imputation to non-response will be applied. If the value for the primary endpoint at Week 48 is available, then such data will be used to determine their response status.

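### Non-study antiviral treatment is both disallowed and to be considered, and the Week 48 estimand does not settle how a value obtained on it is classified

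*Protocol*

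**What the plan says.** **Treatment rules.** Section 6.7, Table 2, lists "Any anti-HBV/HDV drug (including vaccines, interferons) other than the study intervention taken in the context of this study" in the category "Disallowed from 6 months prior to screening until end of follow-up". It makes no exception for participants who have stopped JNJ-3989. Sites must notify the sponsor when a prohibited therapy is given, which is a reporting step and not an exemption.

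Section 7.1 addresses signs of decompensation, or raised direct bilirubin combined with abnormal INR or albumin: "In this case treatment with JNJ-3989 should be discontinued and alternative treatment options (outside the study) should be considered in discussion with the sponsor". Section 2.3.3, for decreasing liver function, says "alternative treatment options outside the study will be considered in discussion with the sponsor".

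Section 7.2 adds: "A participant will NOT be automatically withdrawn from the study if he or she has to discontinue study intervention". Its only listed reasons for withdrawal are loss to follow-up, withdrawn consent and death. For anyone stopping during the double-blind phase, Section 7.1 says: "The participant will enter the follow-up phase and complete the follow-up schedule unless the participant withdraws consent".

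Section 7.1 also requires JNJ-3989/placebo to be stopped for a disallowed medication, but only where the participant does not mean to come off that medication.

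**Estimand rules (Section 9.4.2.1, repeated in the synopsis).**
- 4a: stopping treatment before Week 48 means non-response, with no condition on missing data.
- 4b: non-response applies to "participants who experienced major protocol deviations considered ICE and who have missing ALT and/or HDV RNA data for the primary endpoint at Week 48". This is labelled a composite strategy.
- Missing-data rule: after early discontinuation or a deviation that is an intercurrent event, a missing Week 48 value becomes non-response, and an available value determines response status.
- The SAP is to list the deviations and flag those that are intercurrent events.

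**The concern.** A site that follows Section 7.1 or 2.3.3 and starts another antiviral in a participant who remains in follow-up breaches Table 2. The protocol therefore treats the same act as both a foreseen option and a deviation.

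The statistical consequence is at Week 48. A fall in HDV RNA or a normal ALT reached on another antiviral is not a response to JNJ-3989 + NA or to NA alone. The estimand should say what happens to that value. On one route it gives two opposite answers. On another it gives one answer, that the value counts, under a strategy whose label suggests the opposite. With so few participants, a single classification is visible in the reported proportions.

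**Working it through.** No figure in the plan is contested, so the check is mainly of text.

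**Step 1. Does the ban still cover these participants?** Table 2 runs to the end of follow-up. Sections 7.1 and 7.2 keep a participant who has stopped study intervention in the study and in follow-up. Table 2 has no exception. So it does.

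**Step 2. Classification at Week 48, by route.**

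| Route | Week 48 value | Rule on the intercurrent event | Missing-data rule |
|---|---|---|---|
| Stops JNJ-3989/placebo before Week 48, starts another antiviral | Missing | 4a: non-responder | Non-responder |
| Same | Available | 4a: non-responder | Observed value decides |
| Takes a disallowed antiviral temporarily, stays on study treatment, deviation flagged | Missing | 4b: non-responder | Non-responder |
| Same | Available | 4a and 4b not met | Observed value decides |

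The second row is a contradiction. The fourth is a gap: the observed value decides, and it can be a response. An available value after early discontinuation is plausible, because HDV RNA and liver tests are scheduled repeatedly in follow-up (Section 1.3.3).

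**Step 3. Can the SAP cure it?** Section 9.4.2.1 leaves to the SAP which deviations are flagged. What happens to a flagged deviation is fixed in the protocol. Flagging the antiviral leaves the fourth row unchanged.

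**Step 4. Size.** Part 2 has about 24 versus 6 participants (Section 4.1).
- Active arm: 1/24 = 4.2 percentage points.
- Placebo arm: 1/6 = 16.7 percentage points.

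As an illustration, assume 7/24 versus 0/6 responders, close to the original design rates of 0.30 and 0.04 (0.04 in Section 9.2, plus its 26-point difference). Newcombe 95% intervals:

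| Active | Placebo | Difference (points) | 95% CI |
|---|---|---|---|
| 7/24 | 0/6 | 29.2 | -12.4 to 49.2 |
| 6/24 | 0/6 | 25.0 | -16.1 to 44.9 |
| 7/24 | 1/6 | 12.5 | -29.7 to 36.7 |

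The second row removes one active-arm responder. The third adds one placebo-arm responder.

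**The case against.** The strongest reply is that 4a already covers most of this. The deterioration routes in Sections 7.1 and 2.3.3 run through stopping JNJ-3989/placebo, as does continued use of a disallowed drug. Under 4a all of these participants are non-responders. That stands as a reading of 4a alone. It does not settle the matter, because the missing-data rule expressly covers early discontinuation and says the opposite when a value exists, and because temporary use on study treatment never reaches 4a.

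It is also fair that the alternative treatment is only to be considered, and that no passage says it must be an anti-HDV drug. That reading is natural here, since Section 6.3 allows release of HDV RNA and HBsAg data to support further treatment, but it is an inference.

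Cases should be few. Section 2.2.3 reports that none of the Part 1 participants with ALT elevations showed decreased hepatic function, and Part 2 excludes cirrhosis.

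Three stronger readings are tempting and not supported:
- **That a relapser treated in follow-up is reported as sustained.** The protocol names the sustained-response and relapse endpoints without defining them in detail. Those definitions may be in the SAP.
- **That the bias runs one way, in favour of JNJ-3989.** All 12 Part 1 participants with on-treatment ALT elevations up to Week 48 were on JNJ-3989, so use of other treatment may be uneven. But a false response in the placebo arm lowers the difference.
- **That the 25%-30% response to pegylated interferon in Section 2 gives the chance of a false response.** That figure is undetectable HDV RNA six months after treatment, not the Week 48 composite with normal ALT.

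**Conclusion.** The point holds in a limited form. Table 2 conflicts with Sections 7.1 and 2.3.3 for participants who remain in follow-up, if the alternative treatment is an anti-HBV/HDV drug. In the Week 48 estimand, 4a and the missing-data rule contradict each other after early discontinuation, and a value obtained after temporary use of a disallowed antiviral on study treatment can count as response.

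It would be too strong to say that response on rescue treatment is generally credited: read alone, 4a makes most such participants non-responders. The size is one participant at a time, 4.2 or 16.7 points on the arm rate, assuming about 24 versus 6. No error rate is at stake, because Section 9.1 makes the analyses descriptive. What is at stake is whether the reported proportions mean what they say.

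**What to change.** - **Section 9.4.2.1 and the synopsis:** make 4a and the missing-data rule give the same answer for a participant who stops treatment before Week 48 and has a Week 48 value.
- **Same places:** add one intercurrent event: starting a non-study anti-HDV or anti-HBV drug before the Week 48 assessment is non-response, whether or not Week 48 data exist.
- **Key secondary estimands:** carry both changes over, since Section 9.4.3 builds these estimands in the same way.
- **Disclosure:** state that the change was made after all participants had passed the double-blind phase, as Amendment 5 records, and list any participant whose classification it alters.
- **Table 2 with Sections 7.1 and 2.3.3:** reconcile the passages. Which clinical rule should stand is for the sponsor and investigators.

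The cost is a few lines of text. Concomitant therapies and their duration are already recorded in the CRF (Section 6.7), so no new data are needed. The new intercurrent event can only leave the Week 48 response rates unchanged or lower them.
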